6.3 Data Archival

All reconstructed image data will be transferred to a DICOM archive system for long-term storage. The clinical patient images will be sent to QREADS and MIDIA.

6.4 Patient Confidentiality

All patient image data will be anonymized prior to the image analysis and blinded review. Image data will be sent directly from the scanners to a Mayo Clinic DICOM receiver (a PACS for researchers called Notion, supported by Radiology Informatics) that will anonymize the patient data using predefined rules. In this manner the same patient will have the same anonymization rules applied, independent of when or what system they were scanned on. Both the original and anonymized data are archived in MIDIA and a log that patients that have been anonymized are maintained.

7. Data Safety Monitoring Board (DSMB)

The Principal Investigator (PI) will be responsible for ensuring participants' safety on a daily basis. Monitoring participant safety, evaluate the progress of the study, to review procedures for maintaining the confidentiality of data, the quality of data collection, management, and analyses.

The PI will be informed of serious adverse events as soon as they occur and will notify the NIA and (e.g. DSMB) within 24 hours of notification. The (e.g. DSMB) will meet twice annually, either in-person or by teleconference call to review study progress, data quality, and participants safety

7.1 Human Studies Aspects

Both male and female adult patients will be screened and enrolled in this study. For women of childbearing potential, both pregnancy and breast feeding will be addressed. If a patient has childbearing potential, a pregnancy test will be performed. If the pregnancy test is negative, the scan may proceed. If the pregnancy test is positive, the scan will not proceed and the patient is documented as a screening failure. If a patient is breastfeeding, they are given written instructions to pump and discard their milk or pump and store it for a minimum of 8 hours per the MRI scanning technologist. It is safe for a mother to continue breastfeeding after administration of gadolinium (again instructed to discard for at least 8 hours due to FDG activity as stated above). However, if the mother

desires, she can abstain from breastfeeding for 24 hours with active expression and discarding of breastmilk (7). Sedation will be administered.

No monetary compensation will be provided. All research costs related to this protocol will be paid for by the Department of Radiology.

The MRI results will be recorded in the participant's electronic health record. Because the PET scan portion of the PET/MRI scan is being evaluated, no results will be included in their electronic health record.

8. Budget

All research costs related to this protocol will be paid for by the Department of Radiology. See attached letter from [name] in Appendix 3.

Because this is a novel imaging modality, clinical PET/MR procedure codes that will support FDA and CMS approved indications have yet to be developed and will be based on the results of developmental studies. Radiology RIMS codes specific to this development initiative will be utilized and indicate the study is a development project and there are no patient charges associated with the release of a clinical report. Additionally, Study Coordinator effort will be paid by the Department of Radiology

9. References

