4.3 Patient Scanning Protocol

The PET/MR study consists of an injection of 12 mCi (+/-10%) fluorodeoxyglucose (FDG) and an uptake period of 60 minutes followed by a PET/MRI on the Signa PET/MR system. Patients will need to fast for 18 hours prior to the injection. The patients may require a creatinine check per routine MRI clinical protocol. Patients may request sedation to make the scan more comfortable. They will be given Ativan by mouth to relax by the MR/PET nurse. As per Radiology Departmental policy, the additional MR images obtained during the study will also be given a full clinical read by the staff radiologists to ensure no unexpected findings.

Patients will undergo one scan for this study.

MRI Sequences

1. Sagittal and axial T2 images with fat saturation Lumbar spine
2. Sagittal and axial T1 images with gadolinium and fat saturation lumbar spine
3. A T1 series without fat saturation (volumetric) lumbar spine
4. Axial DWI images lumbar spine

PET images

1. 18F-FDG PET images of the lumbar spine, reformatted in axial and sagittal planes

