7. After each group of up to 5 studies (or fewer), the 2 readers will re-review the studies together to establish consensus and document reasons for interobserver variability.
8. The consensus facet joint scores will then be grouped into 3 categories for comparison to PET data and clinical translation: 1 = normal (0/4), 2= mild peri-facet signal change (1-2/4), 3 = high grade peri-facet signal change (3-4/4).
9. After each group of 5 studies, the 2 readers will re-review the studies together to establish consensus and identify/document reasons for interobserver variability (if any).
10. The overall score for each lumbar facet joint (L1/L2 through L5/S1) will represent the highest of the 2 consensus grades (of T2 fatsat and T1 fatsat with gad).

PET Images

1. Patients will receive a routine clinical dose of F18 FDG and undergo PET imaging at a standard recorded interval.
2. Every lumbar facet joint will be rated as either normal or having increased activity on qualitative visual inspection independently by 2 nuclear medicine physicians on a scale of normal, mildly increased, or markedly increased (high grade).
3. Maximum standard uptake value (SUV-max) will also be determined and will be compared to the SUV-max of the adjacent normal vertebral body (avoiding areas increased in association with degenerative disc disease).
4. The PET readers can view anatomic T1 images for coregistration, but will be blinded to the fat-suppressed MR images/results.
5. After each group of up to 5 studies (or fewer), the 2 readers will re-review the studies together to establish consensus and identify/document reasons for interobserver variability (if any).
6. The consensus rating by visual inspection will establish the qualitative score.

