6.1 Clinical Evaluation after Imaging

The clinician will be serially unblinded to MRI and PET data *in the following sequence* for each patient; this need not be done during an actual patient recheck. The clinician shall remain blinded to the QREADS radiology report. Qualitative scores are used for PET since the MRI scale is qualitative and since quantitative cut-off values for SUV-max do not currently exist:

1. Unblinded to facet joints positive for high-grade MRI change based on overall scores
2. Unblinded to all positive facet joints on MRI based on overall scores (low grade and high grade)
3. Unblinded to facet joints positive for marked FDG PET activity based on qualitative scores
4. Unblinded to all positive facet joints on FDG PET based on qualitative scores (low grade and high grade)

For each of these 4 iterations, the clinician will score if:

1. The data is concordant or discordant with the clinical impression (dichotomous yes/no)
2. The data would change clinical management (dichotomous yes/no)

These 2 scores will be performed with the assumption the biomarker is an accurate predictor of facet joint pain and/or response to percutaneous treatment. Without this assumption, the results would have no impact on management. This will be done independently on each side per patient.

Note that the results could be concordant with clinical impression, but still alter management (for example clinically suspected left L5/S1 facet joint pain with a positive biomarker at only the left L4/L5 facet joint).

Finally, the clinician will indicate which facet joint(s) he/she would specifically prescribe percutaneous treatment for using both clinical and all available PET/MRI data. Note that the PET/MRI data is not an absolute determinant here. The clinician may believe strongly that a facet joint should undergo percutaneous treatment based on clinical data alone.

The actual clinical management is left to the discretion of the clinician for this phase of evaluation. He/she may choose to treat the patient based on clinical information alone or clinical and PET/MRI information. The clinical course including level of pain, response to injections, etc. of the patients may be followed up to 1 year after the PET/MR by chart review for descriptive purposes/analysis, but the patients will not be formally contacted.

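### Suspicious uptake seen on FDG PET but not on the clinical MR read has no stated route back to the patient

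*Combined protocol and SAP*

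**What the plan says.** Section 4.3 (Patient Scanning Protocol) sets out the check for unexpected findings: "the additional MR images obtained during the study will also be given a full clinical read by the staff radiologists to ensure no unexpected findings". It names no such read for PET, although the same section lists "18F-FDG PET images of the lumbar spine, reformatted in axial and sagittal planes" among the images acquired, so tissue outside the facet joints is in view.

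Section 6 (Image Analysis, PET Images) gives the PET readers their task: "Every lumbar facet joint will be rated as either normal or having increased activity on qualitative visual inspection independently by 2 nuclear medicine physicians". They also measure SUV-max and compare it with that of a neighbouring normal vertebral body. They may use anatomic T1 images but not the fat-suppressed MR.

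Section 6.4 (Patient Confidentiality) states: "All patient image data will be anonymized prior to the image analysis and blinded review". It adds: "Both the original and anonymized data are archived in MIDIA and a log that patients that have been anonymized are maintained".

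Section 6.1 returns PET information to the clinician as lists of positive facet joints, after the MRI lists, and withholds the QREADS radiology report during that exercise.

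Section 7.1 puts the MRI results in the health record and says of PET: "Because the PET scan portion of the PET/MRI scan is being evaluated, no results will be included in their electronic health record".

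Section 7 makes the PI responsible for daily participant safety. Its reporting rule names serious adverse events and does not mention imaging findings.

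**The concern.** The plan accepts that a research scan should be checked for unexpected findings, but states that check for only one half of a combined scan. For the other half it goes beyond silence, because 7.1 is an express rule that PET results do not enter the record. A nuclear medicine physician who follows the protocol and sees suspicious uptake has no instruction to note it, no named person to tell, and a rule against filing it.

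The entry criteria do not remove the issue. Section 4.1 excludes suspected spine infection and known osseous malignancy, so undiagnosed disease in patients aged 50 to 100 with back pain can be enrolled. The PET readers must also look beyond the facets, because choosing a normal vertebral body as reference means judging whether a vertebral body is normal.

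What is at stake is participant safety, and whether any early communication is handled in a way that keeps the 6.1 scoring interpretable.

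**Working it through.** The plan gives no figure to reproduce. The check traces the two halves of the scan through the protocol.

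| Step | MR | PET |
|---|---|---|
| Read for unexpected findings (4.3) | Full clinical read by staff radiologists | None stated |
| Research read (6) | Peri-facet grade, synovial enhancement, effusion, DWI | Facet rating and SUV-max |
| State of images at research read (6.4) | Anonymised | Anonymised |
| What reaches the clinician (6.1) | Lists of positive facet joints | Lists of positive facet joints |
| Health record (7.1) | Results recorded | Results kept out |
| Stated trigger, person and step for a suspicious finding | Clinical read and record | None |

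Two situations fall in the gap:

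1. Uptake outside the facet joints that the clinical MR read does not find. It appears in no score and no list.
2. Uptake at a facet joint that looks atypical for facet arthropathy. It does reach the clinician, but only as a positive facet joint, with no means of saying that it looks like something else.

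**Size.** The planned enrolment is n = 10 (section 2). Let r be the proportion of patients with any uptake needing follow-up, and d the fraction of those that the clinical MR read would find. The documents give neither. Treating patients as independent,

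P(at least one unreported case) = 1 − (1 − r(1 − d))^n.

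With d = 0 and an assumed r of 1% to 5%:

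- r = 1%: 1 − 0.99^10 = 1 − 0.904 = 9.6%
- r = 5%: 1 − 0.95^10 = 1 − 0.599 = 40.1%

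Any d above 0 lowers these figures, and d = 1 gives zero. For the assumed rates, about 10% to 40% is therefore an upper bound on the chance that the gap matters in this study.

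**The case against.** The strongest reply is that the gap is narrow. The lumbar spine also gets fat-saturated T2, gadolinium-enhanced T1 and DWI, with a full clinical read. The blinding to PET in section 6 binds the research MRI readers; nothing says that the staff radiologists doing the clinical read are blinded to PET or work on anonymised images. Consent pages and some other passages are missing from the review copy and may cover the return of findings. All of this stands. It limits the point to what the visible text states and to uptake that the clinical MR read does not find.

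Three stronger readings are tempting, and the documents do not support them.

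- *A reader might infer that a finding could never be passed on.* The originals and the log in 6.4 allow re-identification, 6.1 already links PET scores to each patient, and the PI has a general safety duty. The means exist, but the trigger, the person and the step are not stated.
- *A reader might infer that non-facet uptake distorts the 6.2 counts.* The PET scores used for the concordance and management counts are facet-joint scores, so uptake elsewhere is not counted as facet uptake. The 6.1 scores are also made on the assumption that the biomarker is accurate, so they do not test the true source of pain.
- *A reader might infer that reporting such findings leaves the blinding untouched.* Section 6.1 shows MRI before PET. Telling the scoring clinician about PET uptake before that sequence is complete, or filing it where the clinician will see it, discloses PET information early. Any fix has to deal with this.

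The clinical images sent to QREADS (6.3) and the clinical report mentioned in section 8 do not close the gap. Neither section states a clinical read of PET, and 7.1 keeps PET results out of the record.

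**Conclusion.** The point holds as a gap in the visible protocol. The check for unexpected findings is stated for MR only, the PET readers are asked for facet scores and SUV-max on anonymised images, and 7.1 bars PET results from the record. Suspicious uptake found on PET alone has no stated route back to the patient, although the study already holds what is needed to build one.

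The textual finding depends on no rate. Its practical size does: at most about 10% to 40% for at least one case in 10 patients, if 1% to 5% have uptake needing follow-up. That rate is an assumption. The conclusion also rests on the removed pages not already dealing with the matter; if they do, their wording still has to be reconciled with 7.1. This is a participant-safety amendment that should be made, not a flaw in the planned analysis.

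**What to change.** Amend 4.3 and 7.1 as follows.

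1. **Flag.** At the first independent read, one of the two existing nuclear medicine readers marks on the score form whether there is any unexpected or suspicious uptake, including facet uptake that looks atypical for facet arthropathy. The flag should not wait for the consensus session, which is held after groups of up to 5 studies.
2. **Route.** If yes, the coordinator re-identifies the patient from the 6.4 log. The PI ensures that the finding is communicated and filed, under a stated exception to the 7.1 rule.
3. **Unblinding.** Until the 6.1 scores for that patient are complete, the report goes through the PI and not the scoring clinician, where safety allows. Otherwise, record that the clinician was told before scoring and flag that patient in the 6.2 results. The visible text does not show whether the PI is also one of the MRI readers, who are blinded to PET; if so, name a delegate.
4. **Unchanged.** Routine facet PET scores stay out of the record.

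The cost is protocol wording and one field on a form filled in by readers already in the study. The downsides are a few false alarms that need clarification and, occasionally, early unblinding of one patient's scoring.
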